2.1. Study Rationale

This is an exploratory proof of concept randomised, Phase 2a, double-blind, placebo-controlled human challenge study in healthy adults. Participants will receive a single intramuscular dose of either RSVpreF or placebo and 4 weeks later undergo intranasal challenge with RSV-A Memphis 37b virus. The immunogenicity and efficacy of RSVpreF vaccination on virus replication, clinical symptoms, and incidence of symptomatic RSV infection compared to placebo will be evaluated.

This study will serve as a pilot to explore the efficacy of RSVpreF in the human challenge model. Despite the exploratory descriptive nature of the study, a primary objective is included. To explore the primary objective, significant reductions in any one of the three primary endpoints (primary endpoint family) will be explored. The primary endpoint family includes both an objective for a virological endpoint (reduction of area under curve of viral load, VL-AUC) and two subjective clinical based endpoints (reduction in sum total symptom score and incidence of symptomatic infection). Additional key secondary endpoints are included relating to reductions in clinical symptoms (AUC, peak and duration), reduction in mucous secretions, as well as several definitions of incidence of infection and symptomatic infection that include varying degrees of severity of symptoms within their definitions. Furthermore, the baseline immunity of the participants prior to vaccination will be explored in relation to RSVpreF responsiveness, and RSVpreF induced immune responses will be correlated with protection from RSV-A Memphis 37b infection and disease.

2.2. Benefit/Risk Assessment

More detailed information about the known and expected benefits and risks and reasonably expected Adverse Events (AEs) of RSVpreF may be found in the IB.

2.2.1. Risk Assessment

The known risks to participants are detailed below. However, there may also be risks that are unforeseen and not anticipated (e.g., unknown allergies). Every effort will be made to monitor the health of the participants to ensure that such risks are minimised. Trained medical personnel and facilities will be available to provide medical emergency care.

During a pandemic, additional potential risks to participants may include interruptions to study visit schedule, adherence to protocol-specified safety monitoring or safety laboratory assessments. Refer to COVID-19 Crisis Management Plan for further details on the risks and risk mitigation strategy.

Potential Risk of Clinical Significance	Rationale for Risk	Mitigation Strategy
Study Intervention		
Intramuscular Dosing with RSVpreF	Prior studies showed RSVpreF to have an acceptable safety profile as described in Section 2. Signs and symptoms observed after vaccination with RSVpreF include fatigue/tiredness, muscle pain, headache, and joint pain. These were mild or moderate.	These potential reactions, if they are observed, will be monitored but are generally short-term and do not require treatment.
	Local signs and symptoms associated with the injection may include erythema, swelling/induration, and pain/tenderness at the injection site.	Local reactions will be monitored but are generally short-term and do not require treatment.
	Systemic exposure to RSVpreF	To minimise any risks associated with systemic exposure to RSVpreF, male and female participants must be on highly effective contraception methods during the study as described in Section 5.1 .
General Risks related to Vaccines	General signs and symptoms associated with administration of a vaccine, or vaccination with placebo, including fatigue, headache, myalgia, arthralgia, chills and nausea.	These side effects will be monitored but are generally short-term and do not require treatment.
	An allergic reaction to the vaccination may cause a rash, hives or even difficulty breathing. Severe reactions, including anaphylaxis, are rare but can occur with any vaccine.	Medications will be available in the clinic to treat serious allergic reactions promptly. Participants with a known allergy, or history of anaphylaxis or other serious adverse reactions to vaccines or vaccine components will be excluded from the study. The study site should have medical treatment available in case of severe allergic reactions following vaccine administration.

Potential Risk of Clinical Significance	Rationale for Risk	Mitigation Strategy
Study procedures		
Blood Sampling	Pain or bruising at the site where blood is drawn.	Blood samples will be obtained by a trained professional.
	Syncope (fainting) can occur following or even before any blood draw as a psychogenic response to the needle insertion.	Blood samples will be obtained by a trained professional and procedures will be put in place to avoid injury from fainting.
	There is a possibility that in the process of collecting blood a nerve may be injured.	Procedure to be performed by qualified personnel.
	Blood tests performed to address the health of the participants at screening and during the study may indicate that a participant has an infection that he/she was not previously aware of (such as HIV or hepatitis) or an unexpected illness.	The hVIVO doctor will provide the participant's general practitioner (GP), or doctor with a referral letter if the participant agrees.
Nasal sampling	Collection of nasal wash samples or nasopharyngeal swabs may cause discomfort, sneezing, watery eyes, irritated nose or nose bleeding.	Sample collection will be performed by appropriately qualified and trained study staff to minimise the discomfort.

Potential Risk of Clinical Significance	Rationale for Risk	Mitigation Strategy
RSV infection from inoculation		
RSV infection & severe complications	
65% to 85% chance of becoming infected with RSV. Typical RSV illness: abrupt onset of rhinitis, nasal stuffiness, fever, malaise, myalgia (muscle aches), and sore throat.
 
Severe RSV infections are known to occur in both infants and adults. In adult populations, multiple factors, but not older age, are independently associated with severe RSV complications including persons of any age with chronic co-morbidities and significant immune compromise.
 
The study virus, like many viruses, can cause more substantial health issues such as myocarditis (inflammation or damage to the heart muscle). However, the chance of this resulting in serious or permanent changes is rare, as most cases are minor and resolve without any lasting changes. In previous virus challenge studies at hVIVO, uncommonly (3 cases in more than 1000 individuals who have received the challenge virus) blood tests have shown a change suggestive of myocarditis, although in these few participants the blood tests returned to normal without treatment.
	
The safety profile of the RSV-A Memphis 37b challenge strain is well characterised in healthy young adults as this has been used for over ten years by hVIVO. At hVIVO more than 1000 healthy adults aged 18 to 55 years have been challenged with the RSV-A Memphis 37b strain.
 
RSV infection in healthy adults usually resolves without treatment within 7 to 10 days.
 
Strict inclusion and exclusion criteria will apply to ensure only healthy adults are enrolled in this study.
 
There will be a daily medical monitoring in a quarantine unit for at least 12 days post-challenge.
 
Qualified medical and nursing staff in the quarantine unit will monitor for, and manage any symptoms
 
Participants will be closely followed up while being in quarantine. Electrocardiogram will be performed, and cardiac enzymes will be tested at least 4 days, 7 days and 11 days post-viral challenge

	Transient increase in alanine aminotransferase (ALT) or aspartate aminotransferase (AST) without clinical presentation, with a good prognosis upon improvement of infection.	ALT and AST will be monitored.
Transmission of RSV to participants' close contacts	
RSV virus in nasal secretions can cause infection in close contacts.
 
Passing the RSV Challenge Virus to others, including vulnerable people (see below for definition of vulnerable populations).
	
Virus is usually absent from the nose by the time participants are discharged from quarantine. This will be confirmed by testing a nasal sample using a viral diagnostic (e.g. RVAT, PCR) to determine participants' suitability for departure.
 
Participants will remain in individual isolated rooms in the quarantine unit for 12 days after inoculation with the challenge virus.

Potential Risk of Clinical Significance	Rationale for Risk	Mitigation Strategy
		To reduce the risk of transmitting the virus into the community, participants will be asked to avoid, where possible, contact with vulnerable people for 14 days after they leave quarantine (Section 2.2.1.1).
	Passing the RSV Challenge Virus to study staff.	Clinic staff in contact with participants in the quarantine unit will require to wear Personal Protective Equipment (PPE) to avoid the transmission of the RSV Challenge Virus to study staff and to prevent the risk of cross-contamination by a viral disease being brought up into the unit by staff.
Risk of reactivation of herpes infection.	If a participant ever had a herpes infection (e.g., cold sores, genital herpes or shingles), there is a small possibility that this infection could return after challenge.	Participants will be instructed to inform the study staff if they currently have an active herpes infection or have had one during the 30 days before enrolment.
Please consult the IB for detailed information.		

2.2.1.1. Vulnerable Persons

For the purposes of possible contact, a vulnerable individual is a person who has close or household (i.e., share the same apartment or house) high-risk contacts including but not limited to:

- Persons ≥ 65 years of age
- Children ≤ 2 years of age
- Residents of nursing homes
- Women who are pregnant or who are trying to become pregnant.
- Persons of any age with significant chronic medical conditions such as:
 - Chronic pulmonary disease (e.g., severe asthma, Chronic Obstructive Pulmonary Disease (COPD))
 - Chronic cardiovascular disease (e.g., cardiomyopathy, congestive heart failure, cardiac surgery, ischemic heart disease, known anatomic defects)
 - Contacts that required medical follow-up or hospitalisation during the past 5 years because of chronic metabolic disease (e.g., insulin dependent diabetes mellitus, renal dysfunction, haemoglobinopathies)
 - Immunosuppression or cancer
 - Neurological and neurodevelopmental conditions (e.g., cerebral palsy, epilepsy, stroke, seizures)

2.2.2. Benefit Assessment

Healthy participants who receive the study vaccine may not directly benefit from this vaccination as the efficacy of the vaccine has not yet been demonstrated.

Participants may develop some immunity to RSV and benefit from a general health check at Screening. Benefit may also be derived from the medical evaluations and assessments associated with study procedures. In addition, participants are contributing to the process of developing new vaccines in an area of unmet medical need.

2.2.3. Overall Benefit: Risk Conclusion

Taking into account the measures taken to minimise risk to participants in this study, the potential risks identified in association with RSVpreF are justified by the anticipated benefits linked to the evaluation of RSVpreF in the viral challenge model which will subsequently facilitate future assessment of RSV vaccines.

3. Objectives and Endpoints

OBJECTIVES	ENDPOINTS
PRIMARY	

 To evaluate the effect of RSVpreF, in reducing the incidence or severity of infection or disease due to RSV-A Memphis 37b when compared to placebo 	
To evaluate the reduction in one or more of the following endpoints within the primary endpoint family:
 
 Area under the viral load-time curve (VL-AUC) of RSV-A Memphis 37b as determined by qRT-PCR on nasal samples collected twice daily starting two days post-viral challenge (Day +2) up to discharge from quarantine. RT-PCR-confirmed symptomatic RSV infection (Variant 1), defined as: 
 RT-PCR-confirmed RSV infection [two detectable (\geqLLOD) qRT-PCR measurements (reported on 2 or more consecutive days), starting two days post-viral challenge (Day +2) up to discharge from quarantine], AND Either one or more positive clinical symptoms of any grade from two different categories in the symptom scoring system (Upper Respiratory, Lower Respiratory, Systemic), or one Grade 2 symptom from any category Sum total symptoms diary card score: sum total clinical symptoms (TSS) as measured by graded symptom scoring system collected three times daily starting one day post-viral challenge (Day +1) up to discharge from quarantine
SECONDARY	


 To further evaluate the effect of RSVpreF, in reducing the incidence of infection or disease due to RSV-A Memphis 37b, compared to placebo 	
To evaluate the reduction in the following endpoints:
 
 RT-PCR-confirmed symptomatic RSV infection defined as: 
 RT-PCR-confirmed RSV infection (two quantifiable [\geqLLOQ] qRT-PCR measurements (reported on 2 or more consecutive days), starting two days post-viral challenge [Day +2] up to discharge from quarantine.), AND Either one or more positive clinical symptoms of any grade from two different categories in the symptom scoring system (Upper Respiratory, Lower Respiratory, Systemic), or one Grade 2 symptom from any category Culture lab-confirmed reduction of symptomatic RSV infection defined as: 
 Lab-confirmed culturable RSV infection (one quantifiable (\geqLLOQ) viral culture measurement starting two days post-viral challenge (Day +2) up to discharge from quarantine), AND Either one or more positive clinical symptoms of any grade from two different categories in the symptom scoring system (Upper Respiratory, Lower Respiratory, Systemic), or one Grade 2 symptom from any category

 To further evaluate the effect of RSVpreF, in reducing infection due to RSV-A Memphis 37b compared to placebo 	
To evaluate the reduction in the following endpoints:
 
 Peak viral load of RSV-A Memphis 37b as defined by the maximum viral load determined by quantifiable qRT-PCR measurements in nasal samples starting two days post-viral challenge (Day +2) up to discharge from quarantine. Peak viral load of RSV-A Memphis 37b as defined by the maximum viral load determined by quantitative viral culture measurements in nasal samples starting two days post-viral challenge (Day +2) up to discharge from quarantine. Duration of RSV-A Memphis 37b quantifiable qRT-PCR measurements in nasal samples starting two days post-viral challenge (Day +2) up to discharge from quarantine. Duration is defined as the time (hours) from first detectable until first confirmed undetectable assessment after their peak measure (after which no further virus is detected). Duration of RSV-A Memphis 37b quantitative RSV viral culture measurements in nasal samples starting two days post-viral challenge (Day +2) up to discharge from quarantine. Duration is defined as the time (hours) from first detectable until first confirmed undetectable assessment after their peak measure (after which no further virus is detected). Area under the viral load-time curve (VL-AUC) of RSV-A Memphis 37b as determined by quantitative viral culture on nasal samples starting two days post-viral challenge (Day +2) up to discharge from quarantine


 To further evaluate the effect of RSVpreF, in reducing symptomatic infection due to RSV-A Memphis 37b, compared to placebo 	
To evaluate the reduction in the following endpoints:
 
 Area under the curve over time (TSS-AUC) of total clinical symptoms (TSS) as measured by graded symptom scoring system (categorical and visual analogue scales) collected three times daily starting one day post-viral challenge (Day +1) up to discharge from quarantine. Peak symptoms diary card score: peak total clinical symptoms (TSS) as measured by graded symptom scoring system (categorical and visual analogue scales) collected three times daily starting one day post-viral challenge (Day +1) up to discharge from quarantine Peak daily symptom score: Individual maximum daily sum of Symptom score starting one day post-viral challenge (Day +1) up to the end of quarantine. Number (%) of participants with Grade 2 or higher symptoms

 To evaluate the effect of RSVpreF, in reducing the incidence of RSV-A Memphis 37b infection compared to placebo 	
To evaluate the reduction in the following endpoints:
 
 Occurrence of at least two positive quantifiable (\geqLLOQ) qRT-PCR measurements in nasal samples at different timepoints reported on 2 or more consecutive days starting two days post-viral challenge (Day +2) up to discharge from quarantine. Occurrence of at least two positive detectable (\geqLLOD) qRT-PCR measurements in nasal samples at different timepoints reported on 2 or more consecutive days starting two days post-viral challenge (Day +2) up to discharge from quarantine. Occurrence of at least one positive quantitative (\geqLLOQ) cell culture measurement in nasal samples starting two days post-viral challenge (Day +2) up to discharge from quarantine.

 To evaluate the effect of RSVpreF, in reducing nasal discharge, when compared to placebo 	
To evaluate the reduction in the following endpoints:
 
 Total weight of mucus produced starting one day post-viral challenge (Day +1) up to discharge from quarantine. Total number of tissues used by participants starting one day post-viral challenge (Day +1) up to discharge from quarantine.

 To evaluate the safety and reactogenicity of RSVpreF, when compared to placebo 	
To evaluate the incidence of the following endpoints:
 
 Occurrence of solicited local reactions and systemic events within 7 days (i.e., on the day of vaccination and 6 subsequent days) after vaccination. Occurrence of unsolicited adverse events (AEs) within 30 days (i.e., on the day of vaccination and 29 subsequent days) after vaccination Occurrence of medically attended AEs (MAEs) and serious adverse events (SAEs) from vaccination (Day -28) up to study end (Day +155).

 To evaluate the safety of the RSV challenge model. 	
To list the incidence of the following endpoints:
 
 Occurrence of unsolicited AEs within 30 days post-viral challenge (Day 0) up to Day +28 follow up. Occurrence of SAEs related to the viral challenge from the viral challenge (Day 0) up to Day +28 follow up. Occurrence of haematological and biochemical laboratory abnormalities during the quarantine period. Use of concomitant medications within 30 days post-viral challenge (Day 0 up to Day +28 follow up).
TERTIARY	
Tertiary/exploratory endpoints include but are not limited to the following.	

 To evaluate the effect of baseline immune status on immunogenicity and efficacy of the RSVpreF, when compared to placebo 	
 The primary, secondary, and tertiary endpoints may be explored in relation to the baseline status of participants and the response to vaccination.

 To characterize the innate, humoral and cellular immunity at a) baseline (prior to RSVpreF administration), b) after RSVpreF administration, and c) after RSV-A Memphis 37b challenge 	
The primary, secondary, and tertiary endpoints may be explored in relation to immunological levels at baseline, after vaccination, and after RSV challenge. Assays performed on serum and nasal samples may include, but are not limited to:
 
 Humoral immunity / systems serology (for example RSV A & B neutralizing titres, PreF and PostF ELISAs to IgG, IgA, sIgA, ADCC) Immunological measures of RSV A & B exposure/infection in community post vaccination Proteomic levels and changes (for example, cytokine and chemokines) Cellular cell quantification and quality of immunity (for example T and B cell frequencies, phenotypes and functionality assays: ELISPOTs, ICS, cytokine/chemokine responses) Transcriptome levels and changes (for example, RNAseq, single cell RNAseq, microarray, PCR) Genomics in relation to RSV susceptibility, infection and vaccine responsiveness (e.g. HLA typing, SNPs, GWAS)

To evaluate the effect of RSVpreF, in reducing the incidence of RSV-A Memphis 37b disease, when compared to placebo	
To evaluate the reduction in the incidence of:
 
Upper Respiratory Tract illness (URT)Lower Respiratory Tract illness (LRT)Systemic illness (SI)Febrile illness (FI)Proportion of Participants with Grade 2 or higher symptoms on any occasion at any time from the last assessment on Day 0 to quarantine dischargeProportion of participants with Grade 2 or higher Symptoms on two separate occasions at any time from the last assessment on Day 0 to quarantine dischargeProportion of participants with any symptom (grade ≥ 1) on any occasion at any time from the last assessment on Day 0 to quarantine dischargeProportion of participants with any symptom (grade ≥ 1) on two separate occasions at any time from the last assessment on Day 0 to quarantine discharge
---	--

4. Study Design

4.1. Overall Design

This is a randomised, Phase 2a, double blind, placebo-controlled study to evaluate the safety, immunogenicity and efficacy of an RSV vaccine against RSV-A Memphis 37b infection in healthy participants.

The total duration of study participation for a participant is approximately 6 months after vaccination, with the following sequence and duration of study periods:

Screening Phase:

- Screening prior to vaccination from Day -84 to Day -29 (Day -118 for RSV serology) Pre-screening data collected through the hVIVO generic screening process prior to signing the study specific consent form, and prior to vaccination from Day -84 to Day -29 (Day -118 for RSV serology) may be transferred to this study after study-specific consent form has been signed by the participant. Pre-screening data obtained prior to this window can be re-assessed any time prior to vaccination from Day -84 to Day -29.

Vaccination Phase:

- Vaccination on Day -28 (± 3 days), participants will be randomised 1:1 to receive RSVpreF or placebo
- Follow up clinic visit 1 day post vaccination
- Follow up clinic visit 7 days post vaccination (± 1 day)

Quarantine Phase:

- Admission to the Quarantine Unit on Day -2/-1; resident in the Quarantine Unit for approximately 15 days, from admission on Day -2 to planned discharge on Day +12.
- Challenge with Challenge Virus on Day 0.
- Discharge from quarantine planned on Day +12

Follow-Up Phase:

- Day +28 (± 3 days).
- Day +155 (± 14 days)

Participants will be pre-screened for susceptibility to RSV infection, i.e., have levels of RSV neutralising antibodies compatible with susceptibility to RSV infection.

Participants will be randomised to receive a single intramuscular dose of RSVpreF or Placebo on Day -28 (± 3 days):

- **Reference article product**
 - PF-06928316 also known as RSVpreF
 - Dose: 120mcg

- **Placebo product**

- Placebo to match vaccine

All participants will be closely observed for a minimum of 30 minutes post-vaccination, to monitor for the development of any acute reactions, or longer if deemed necessary by the investigator. Any unsolicited, solicited AEs and vital signs will be documented by study-site personnel following this observation period. Participants will be given a thermometer, a calliper/ruler and a vaccination diary card [VDC] (for daily assessment of symptoms) with instructions for the completion of the diary card. Each participant will record the presence/absence of symptoms, solicited AEs, and oral temperatures, beginning on the evening of the study vaccine dosing day (Day -28) and daily for a total of 7 days. Reminders (e.g. via text message will be sent to participants from study site personnel to ensure compliance with the VDC. A study site personnel will collect and review the participant completed vaccination diary card at the post-vaccination clinic visit, approximately 7 days post vaccination and review the information and confirm the entries. Participants will be provided with an Emergency Contact Card to contact the Investigator when potentially severe reaction occurs.

Post-vaccination clinic visits will occur 1 day post vaccination and approximately 7 days post-vaccination. Any unsolicited, solicited AEs and vital signs will be documented by the Investigator. Any clinically significant symptom/AE persisting after the 7 days will be followed up by the Investigator until resolution or until clinically stable outcome is reached.

One to two days prior to viral challenge, participants will be admitted to the quarantine unit. Quarantine assessments will include relevant information since vaccination, ECG, Spirometry, Physical Examination and clinical laboratory testing. Participants will subsequently receive the following on Day 0:

- **RSV challenge virus**

- RSV-A Memphis 37b, total dose of approximately $4.5 \log_{10}$ plaque forming unit, given intranasally

Participants will reside in the Quarantine Unit for a total of approximately 15 days (from Day -2 to Day 12). From Day 2 to Day 11, nasal samples will be collected approximately every 12 hours, and physical examination, vital signs measurements, ECG, clinical safety laboratory test, and Spirometry will be performed as per the Schedule of Activities (SOA) in [Section 1.3](#). Release from quarantine is foreseen at Day 12, provided no virus is detected (by either the qualitative virus antigen test (RVAT) or equivalent viral test, as appropriate) and the participant has no clinically significant symptoms. If the participant continues to have clinically significant symptoms and/or detectable virus on Day 12, additional extended quarantine stay may be required based on the assessment of the Investigator. If appropriate, participants may reside in quarantine for an additional night or longer before discharge.

Participants will attend a follow up visit at 28 days post-challenge (Day 28), and a follow-up visit at 6 months post-vaccination.

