10.3.12. Reactogenicity Data

Reactogenicity data are solicited AEs collected using the VDC, starting on the day of vaccination through 7 days post vaccination. The reactogenicity data will include local reactions (redness, swelling, and pain at the injection site) and systemic events (fever, fatigue, headache, vomiting, nausea, diarrhea, muscle pain, and joint pain).

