For each local reaction, the derivation of whether or not the specific reaction occurred on "any day (Day 1-7)" will be made. The derivation of this variable is given in Table 10 below.

Table 10 Derived Variables for Each Local Reaction

Variable ^a	Yes (1)	No (0)	Missing (.)
Any day (Day 1-7)	Participant reports the reaction as "Yes" on any day from Day 1 through Day 7.	Participant reports the reaction as "No" on all 7 days or as a combination of "No" and missing on all 7 days.	Participant reports the reaction as missing on all 7 days.

a. The variable will be defined for each of the 3 local reactions.

For "any local reaction" on any day, a similar definition can be applied, as given in Table 11 below.

Table 11 Derived Variables for Any Local Reaction

Variable	Yes (1)	No (0)	Missing (.)
Any day (Day 1-7)	Participant reports any redness or swelling >2.0 cm or "Yes" for pain at injection site on any day during Days 1 through 7.	Participant reports redness or swelling ≤2.0 cm or pain at injection site as "No" on all 7 days or as a combination of above and missing on all 7 days for all 3 local reactions.	Participant reports all of the local reactions as missing on all 7 days.

- **Maximum Severity for Local Reactions**

The maximum severity (highest grading) of each local reaction within 7 days after vaccination will be derived. The maximum severity will be derived as follows:

- = "Missing," if values are missing for all days from Days 1 through 7;
- = 0, if the participant reports all reactions as "No" or a combination of missing and "No" for all days from Days 1 through 7;

= *highest grade* (maximum severity) within 7 days after vaccination, if the answer is not "No" for at least 1 day.

- **Duration of Each Local Reaction**

The duration of each local reaction will be calculated in days as (resolution date of reaction - start date of reaction + 1). Resolution of the reaction is the last day on which the reaction is recorded in the VDC or the date the reaction ends if it is unresolved during the participant diary-recording period (end date collected on the CRF), unless chronicity is established. If there is no known end date, the duration will be considered unknown and set to missing.

- **Onset of Local Reaction**

The onset day of each local reaction and any local reaction will be derived.

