Nausea	Does not interfere with activity	Some interference with activity	Prevents daily routine activity	Emergency room visit or hospitalisation for severe nausea
Diarrhea	2 to 3 loose stools in 24 hours	4 to 5 loose stools in 24 hours	6 or more loose stools in 24 hours	Emergency room visit or hospitalisation for severe diarrhea
Muscle pain	Does not interfere with activity	Some interference with activity	Prevents daily routine activity	Emergency room visit or hospitalisation for severe muscle pain
Joint pain	Does not interfere with activity	Some interference with activity	Prevents daily routine activity	Emergency room visit or hospitalisation for severe joint pain

The highest temperature for each day for 7 days after vaccination is to be recorded in the VDC. For reporting purposes, fever will be analysed using the grading scale in Table 13.

Table 13 Grading Scale for Fever in the VDC

Mild Grade 1	Moderate Grade 2	Severe Grade 3	Grade 4
≥38.0°C to 38.4°C	>38.4°C to 38.9°C	>38.9°C to 40.0°C	>40.0°C

The presence or absence of each systemic event on a given day is defined as follows:

- = “Missing,” if the value is missing on a given day;
- = “Yes,” if the participant reports a temperature ≥38.0°C for fever **or** “Mild,” “Moderate,” “Severe,” or “Grade 4” for the remaining events on a given day;
- = “No,” if the participant reports a temperature <38.0°C for fever **or** “None” for the remaining events on a given day.

For each systemic event, the following variables will be derived:

1. Presence or absence of each systemic event on each day (Days 1-7) after vaccination.
2. Presence or absence of each systemic event on “any day (Day 1-7)” after vaccination.
3. Maximum severity of each systemic event on “any day (Day 1-7)” after vaccination.
4. Presence or absence of any systemic event on “any day (Day 1-7)” after vaccination.
5. Duration of each systemic event after vaccination.
6. Onset day of each systemic event after vaccination.
7. Onset day of any systemic event after vaccination.

The derivation of these variables is similar to the derivation of the variables for local reactions ([Section 10.3.13](#))

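### A diary card handed in at an in-window visit six days after vaccination can lack a full seventh entry, so a reaction first appearing after that visit drops out of the 7-day reactogenicity tabulation

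*Combined protocol and SAP*

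**What the plan says.** Write V for the vaccination day.

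- **Endpoint.** Section 3 lists among the secondary safety endpoints: "Occurrence of solicited local reactions and systemic events within 7 days (i.e., on the day of vaccination and 6 subsequent days) after vaccination". That is V to V+6.
- **Diary schedule.** Section 4.1 has participants record symptoms and temperature "beginning on the evening of the study vaccine dosing day (Day -28) and daily for a total of 7 days"; Section 8.17.2.1 says much the same. Section 10.3.12.2 adds: "The highest temperature for each day for 7 days after vaccination is to be recorded in the VDC".
- **Collection.** Section 4.1 has the site take the card in at the week-one visit: "A study site personnel will collect and review the participant completed vaccination diary card at the post-vaccination clinic visit, approximately 7 days post vaccination". The same section lists that visit as "Follow up clinic visit 7 days post vaccination" with a tolerance of one day either way, and the Schedule of Activities (Section 1.3) gives the same window.
- **Derivation.** Section 10.3.12.1 codes a day without a value as 'Missing'. Table 10 sets the any-day variable to 'No' when the reaction is reported as 'No' "on all 7 days or as a combination of" 'No' and missing. The maximum-severity rule gives 0 for the same mixture. Section 10.3.12.2 derives systemic events in a similar way.
- **Window wording elsewhere.** Section 10.3.12 describes diary collection as "starting on the day of vaccination through 7 days post vaccination", and note k of the Schedule of Activities also runs collection until 7 days after vaccination.

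**The concern.** The visit window and the diary schedule overlap at one point. The seventh entry belongs to V+6, and V+6 is also the earliest permitted visit day. A card collected that morning or afternoon cannot hold an evening entry for the same day. If the participant fills in the line before handing the card over, it cannot reflect the hours still to come, including that day's highest temperature.

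The derivation rules then treat an otherwise clean card as showing no reaction. The consequence runs one way: incidence and maximum severity can be understated, never overstated. This is a safety endpoint, and one purpose of the trial is to describe the vaccine's reactogenicity against placebo, so an avoidable downward error is worth removing even if it is small.

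**Working it through.** **Inputs.** Endpoint window V to V+6 (Section 3). First entry on the evening of V, seven daily entries (Sections 4.1 and 8.17.2.1). Visit on V+6, V+7 or V+8 (Sections 1.3 and 4.1). Any-day and maximum-severity rules (Section 10.3.12.1). Up to 72 vaccinated at 1:1 (Sections 9.2 and 6.3), so 72/2 = 36 per arm.

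**1. Reproduce the planned number of entries.** Evenings V+0 to V+6 give 7 entries, matching the seven days stated in the endpoint.

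**2. Count the evening entries that exist before a daytime visit.**

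| Visit day | Evening entries completed |
|---|---|
| V+6 | 6 of 7 |
| V+7 | 7 of 7 |
| V+8 | 7 of 7 |

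Only the first entry is explicitly an evening one. Evening timing for the later entries is inferred from the daily schedule and from the request for each day's highest temperature. If a V+6 attender writes the last entry before the visit, all 7 exist, but the seventh covers only part of its day.

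**3. Apply Table 10 with Day 7 missing.** For one reaction there are 2^7 = 128 yes/no patterns over seven days. Setting Day 7 to missing changes the any-day result in exactly one: 'No' on Days 1–6 and 'Yes' on Day 7, which is derived as 'No' instead of 'Yes'. This counts patterns; it is not a probability. Separately, maximum severity is understated whenever the highest grade would have fallen on Day 7, including in participants who already count as reactors.

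**4. Look for a later capture.** No section describes return of the card after the visit, a call about the last entry, or a completeness requirement. With vaccination on its nominal Day −28, a V+6 visit falls on Day −28 + 6 = −22. The next scheduled attendance is quarantine admission on Day −2 or −1, 20 or 21 days later.

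**5. Size.** The documents give neither the share attending on V+6 (f) nor the share of vaccinees whose first reaction starts on Day 7 (q). Both are assumptions. If attendance day is unrelated to late onset, and onset falls after the visit:

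understatement of incidence = f × q

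| f | q | Percentage points | Participants per arm of 36 |
|---|---|---|---|
| 10% | 0.5% | 0.05 | 36 × 0.0005 = 0.02 |
| 1/3 | 1% | 0.33 | 36 × 0.0033 = 0.12 |
| 100% | 5% | 5 | 36 × 0.05 = 1.8 |

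In the middle case, the chance of missing at least one reactor in an arm is 1 − (1 − 0.0033)^36 ≈ 11%.

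**The case against.** The best defence is that the plan intends a full card. Section 4.1 speaks of a card the participant has completed and of an approximate seven days. Section 8.11.1 and the Schedule of Activities require only review at the visits, and reminders are sent. Nothing tells staff to take a card early. All of this is fair, but a V+6 visit remains compliant, the card is to be collected there, and no instruction covers an outstanding entry.

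It is also fair that Sections 8.17.1 and 10.3.6.1 collect all adverse events to the end of the study, so a late reaction need not vanish from the safety data. It would still be outside the solicited tabulation, because Section 10.3.12 defines reactogenicity data as what the diary collects. Section 9.5 leaves the treatment of missing data to the SAP, but no analysis rule recovers an entry that was never made.

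Several stronger readings are tempting, and the documents do not support them:

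- *The missing day is itself scored as no reaction.* Section 10.3.12.1 keeps the day as 'Missing'. It is the any-day summary that becomes 'No', and only if every observed day is 'No'.
- *The endpoint is cut short for everyone.* At V+7 and V+8 all seven entries exist.
- *Resolution dates and durations are truncated.* Sections 8.17.2.1 and 10.3.12.1 have end dates of reactions continuing past the diary period recorded on the CRF.
- *The window is really eight days, so even an on-time visit is too early.* That rests on the looser wording in Section 10.3.12 and note k. The endpoint definition, the seven-day diary and the Day 1–7 derivations all point to seven.
- *The arms are distorted differently.* Visits are blinded, and no difference in attendance by arm is shown.

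**Conclusion.** The gap is real but narrow. It applies only to participants seen on V+6. For them it can turn a first reaction appearing after the visit into an any-day 'No' with severity 0, and it can understate a peak grade on that day. The error always lowers reported reactogenicity.

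The effect on incidence is probably small: about 0.3 percentage points in the middle case, within an assumed range of 0.05 to 5. The upper end requires every participant to attend on V+6 and 5% to have first onset on Day 7. The endpoint is secondary and summarised descriptively, so no primary conclusion depends on it. This is a low-cost improvement and not a flaw that threatens the trial. The inconsistent window wording should be tidied at the same time, but it does not enlarge the effect.

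**What to change.** Collect the card only once the seventh entry has been made. Either change would do this:

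- set the visit window to 7 days (0/+1 day); or
- keep ±1 day, but let V+6 attenders keep the card and return it later, or confirm the last entry with the site.

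The first costs one day of scheduling flexibility and the second one extra contact. Under either, all seven entries can be complete when the card is taken in.

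Reconcile Section 10.3.12 and note k of the Schedule of Activities with the endpoint window in Section 3 ("on the day of vaccination and 6 subsequent days").

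Leave the Table 10 rule as it is. Accepting 'No' only when the last day was observed would drop non-reactors with a gap but keep reactors with the same gap. As an illustration with assumed values, take 30% true incidence and 20% of last days unconfirmed at random. Retained non-reactors are 0.70 × 0.80 = 0.56, so estimated incidence is 0.30/(0.30 + 0.56) = 34.9%. That is 4.9 points too high, well above the 0.3 points in the middle case here.
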